6.2.4. Derived Data

- Age (year), derived using first dose date as the reference start date and July 1st of birth year and truncated to a whole-year (integer) age. Patients whose derived age is less than 18 will have the required minimum age of 18 at informed confirmed; reporting for age, age groups, and lab ranges, however will be based on their derived age.
- Age group (<65, ≥65 years old)
- Age group (<65, ≥65 to <75, ≥75 to <85, ≥85 years old)
- Body mass index (BMI) (kg/m^2) = $\text{Weight (kg)} / ((\text{Height (cm)} / 100)^2)$
- BMI category (<25 kg/m^2 , ≥25 to <30 kg/m^2 , ≥30 kg/m^2)
- The duration of AD from diagnosis (years) = $[(\text{Date of informed consent} - \text{Date of AD diagnosis}) + 1] / 365.25$.
 - If year of onset is missing, duration of AD will be set as missing. Otherwise, unknown month will be taken as January, and unknown day will be taken as 01. The duration of AD will be rounded to 1 decimal place.
- Duration of AD (years) category (0 to <2 years, 2 to <5 years, 5 to <10 years, 10 to <20 years, ≥20 years)
- Diagnosis age (years), derived using diagnosis date as the reference start date and July 1st of birth year and truncated to a whole-integer age.
- Diagnosis age group (<18, ≥18 to <50, ≥50 years old)
- Change from baseline = postbaseline measurement at Visit x – baseline measurement.
 - If a baseline value is missing, it will not be imputed and the change from baseline will not be calculated.
- Percent change from baseline at Visit x:
 $((\text{Post-baseline measurement at Visit x} - \text{Baseline measurement}) / \text{Baseline measurement}) * 100$.
 - If a baseline value is missing, it will not be imputed and percent change from baseline will not be calculated.
- Weight (kg) = weight (lbs) * 0.454.
- Weight category (<60 kg, ≥60 to <100 kg, ≥100 kg)
- Height (cm) = height (in) * 2.54.
- Cyclosporine inadequate efficacy (yes, no)
 - Set **yes** if the reason for discontinuation is inadequate response.
- Cyclosporine intolerance (yes, no)

- Set **yes** if the reasons for discontinuation are: intolerance to medication or contraindication (Physician indicated cyclosporine was used and a contraindication was noted).
- Cyclosporine contraindication [ineligible] (yes, no)
 - Set to **yes** if cyclosporine never used because of a contraindication
- Cyclosporine inadvisable (yes, no)
 - Set to **yes** if the following reasons were selected for either not using the medication or discontinuing the medication:
 - Reason for not using medication: Physician decision, concern about side effects, unfavorable benefit risk, contraindication.
 - Reasons for discontinuation: inadequate response, intolerance to medication, or contraindication.
- TCNI inadequate efficacy (yes, no)
 - Set **yes** if the reason for discontinuation is inadequate response.
- TCNI intolerance (yes, no)
 - Set **yes** if the reasons for discontinuation are: intolerance to medication or contraindication (Physician indicated TCNI was used and a contraindication was noted).
- TCNI contraindication / [ineligible](yes, no)
 - Set to **yes** if TCNI never used because of a contraindication
- TCNI inadvisable (yes, no)
 - Set to **yes** if the following reasons were selected for either not using the medication or discontinuing the medication:
 - Reason for not using medication: Physician decision, concern about side effects, unfavorable benefit risk, contraindication.
 - Reasons for discontinuation: inadequate response, intolerance to medication, or contraindication.

6.3. Covariate Adjustment

The randomization to treatment groups at Week 0 (Visit 2) is stratified by disease severity (IGA) and geographic region as described in Section 5.1. Unless otherwise specified, the statistical analysis models will adjust for these stratification variables. The covariates used in the logistic model for categorical data will include the parameter value at baseline. The covariates used in the ANCOVA model for continuous data will include the parameter value at baseline. Inclusion of baseline in the model ensures treatment LSM are estimated at the same baseline value. When an MMRM analysis is performed, baseline value and baseline-by-visit interactions will be included as covariates.

6.4. Handling of Dropouts or Missing Data

Intercurrent events (ICH E9 R1) are events which occur after the treatment initiation and make it impossible to measure a variable or influence how it would be interpreted.

Depending on the estimand being addressed, different methods will be used to handle missing data as a result of intercurrent events. Intercurrent events can occur through the following:

- application of one of the censoring rules (including after permanent study drug discontinuation or after rescue therapy)
- discontinuation
- missing an intermediate visit prior to discontinuation or rescue
- lost to follow-up.

Non-censor intercurrent events are events that are not due to the application of any censoring rule, i.e., the last 3 items in the list above.

Note that as efficacy and health outcome data can accrue after a patient permanently discontinues study drug or begins rescue therapy, specific general censoring rules to the data will be applied to all efficacy and health outcome observations subsequent to these events depending on the estimand being addressed. These specific censoring rules are described below.

The *primary censoring rule* will censor efficacy and health outcome data after permanent study drug discontinuation or after rescue therapy. This censoring rule will be applied to all continuous and categorical efficacy and health outcome endpoints. This censoring rule is equivalent to using all the data up to rescue.

A *secondary censoring rule* will only censor efficacy and health outcome data after permanent study drug discontinuation. This sensitivity analysis will include all observed values up to study drug discontinuation. The secondary censoring rule will be applied to primary and key secondary efficacy and health outcome endpoints as sensitivity analyses.

[Table JAHM.6.1](#) describes the planned imputation methods for efficacy and health outcome endpoints with associated censoring rules. Sections [6.4.1](#) through [6.4.5](#) summarize the methodology of each imputation rule.

Table JAHM.6.1. Imputation Techniques for Various Variables

Efficacy and Health Outcome Endpoints	Imputation Method
IGA(0,1), EASI75, 4-point Itch NRS improvement, EASI90, SCORAD75	NRI ^{ab} , pMI ^a , Tipping point ^a
EASI percent change, ADSS Item 2 change, Skin Pain NRS change	MMRM ^{ab} , mLOCF ^a , pMI ^a
All remaining categorical measures	NRI ^a
All remaining continuous efficacy and health outcome measures	MMRM ^a , mLOCF ^a

Abbreviations: ADSS = Atopic Dermatitis Sleep Scale; EASI = Eczema Area and Severity Index score; IGA = Investigator's Global Assessment for AD; mLOCF = modified last observation carried forward; MMRM = mixed model repeated measures; NRI = nonresponder imputation, NRS = Numeric Rating Scale; pMI = placebo multiple imputation; SCORAD = SCORing Atopic Dermatitis.

^a Analyses utilizing the primary censoring rule.

^b Analyses utilizing the secondary censoring rule.

6.4.1. Nonresponder Imputation

A NRI method imputes missing values as non-responses and can be justified based on the composite strategy for handling intercurrent events (ICH E9 R1). This imputation procedure assumes the effects of treatments disappear after the occurrence of an intercurrent event defined by the associated censoring rule.

All categorical endpoints will utilize the NRI method after applying the primary censoring rule to patients who permanently discontinued study drug or were rescued (described in Section 6.4). Additionally, all primary and key secondary categorical endpoints will utilize NRI after applying the secondary censoring rule as sensitivity analyses. For analyses which utilize either of the censoring methods, randomized patients without at least 1 post-baseline observation will be defined as nonresponders for all visits.

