4.2.2. Other Secondary Objectives

These are prespecified objectives that will not be adjusted for multiplicity.

Objectives	Endpoints
To test the hypothesis that baricitinib 1-mg QD, 2-mg QD, or 4-mg QD is superior to placebo in the treatment of patients with moderate to severe AD.	
 • Proportion of patients achieving IGA of 0 or 1 with a ≥ 2-point improvement at Week 4
To compare the efficacy of baricitinib 1-mg QD, 2-mg QD, or 4-mg QD to placebo in AD during the 16-week double-blind placebo-controlled period as measured by physician-assessed signs and symptoms of AD.	
 • Proportion of patients achieving EASI50 at 16 weeks • Proportion of patients achieving IGA of 0 at 16 weeks • Mean change from baseline in SCORAD at 16 weeks • Proportion of patients achieving SCORAD90 at 16 weeks • Mean change from baseline in BSA affected at 16 weeks • Proportion of patients developing skin infections requiring antibiotic treatment by Week 16
To compare the efficacy of baricitinib 1-mg QD, 2-mg QD, or 4-mg QD to placebo in AD during the 16-week, double-blind, placebo-controlled treatment period as assessed by patient-reported outcome/QoL measures.	
 • Percent change from baseline in Itch NRS at 1 week and 16 weeks • Mean change from baseline in Itch NRS at 4 weeks and 16 weeks • Mean change from baseline in the total score of the POEM at 16 weeks • Mean change in the PGI-S-AD scores at 16 weeks • Mean change from baseline in HADS at 16 weeks • Mean change in the DLQI scores at 16 weeks • Mean change in the WPAI scores at 16 weeks • Mean change in the EQ-5D-5L scores at 16 weeks

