		ANCOVA using mLOCF	ITT	Bari 4-mg or Bari 2-mg or Bari 1-mg vs PBO; Week 16	Sensitivity analysis
		pMI and Tipping Point	ITT	Bari 4-mg or Bari 2-mg or Bari 1-mg vs PBO; Week 16	Sensitivity analysis
	
 Proportion of patients achieving EASI50 Proportion of patients achieving EASI75 Proportion of patients achieving EASI90 	Logistic regression using NRI	ITT	Bari 4-mg or Bari 2-mg or Bari 1-mg vs PBO; Week 16	Secondary analysis
			ITT	Bari 4-mg or Bari 2-mg or Bari 1-mg vs PBO; Week 16	Key secondary analysis
		Logistic regression using NRI	PPS	Bari 4-mg or Bari 2-mg or Bari 1-mg vs PBO; Week 16	Sensitivity analysis
			pMI and Tipping Point	ITT	Bari 4-mg or Bari 2-mg or Bari 1-mg vs PBO; Week 16
		Body Surface Area (BSA) Affected by AD	
 BSA score Change from baseline in BSA score 	MMRM	ITT
ANCOVA using mLOCF	ITT			Bari 4-mg or Bari 2-mg or Bari 1-mg vs PBO; Week 16	Sensitivity analysis

Measure	Variable	Analysis Method (Section 6.2.3)	Population (Section 6.2.1)	Comparison/Time Point	Analysis Type
SCORing Atopic Dermatitis (SCORAD)	
 • SCORAD score • Change from baseline in SCORAD score 	MMRM	ITT	Bari 4-mg or Bari 2-mg or Bari 1-mg vs PBO; Week 16	Secondary analysis
		ANCOVA using mLOCF	ITT	Bari 4-mg or Bari 2-mg or Bari 1-mg vs PBO; Week 16	Sensitivity analysis
	Proportion of patients achieving SCORAD75	Logistic regression using NRI	ITT	Bari 4-mg or Bari 2-mg or Bari 1-mg vs PBO; Week 16	Key secondary analysis
			PPS	Bari 4-mg or Bari 2-mg or Bari 1-mg vs PBO; Week 16	Sensitivity analysis
		Logistic regression using pMI	ITT	Bari 4-mg or Bari 2-mg or Bari 1-mg vs PBO; Week 16	Sensitivity analysis
	Proportion of patients achieving SCORAD90	Logistic regression using NRI	ITT	Bari 4-mg or Bari 2-mg or Bari 1-mg vs PBO; Week 16	Secondary analysis
		pMI and Tipping Point	ITT	Bari 4-mg or Bari 2-mg or Bari 1-mg vs PBO; Week 16	Sensitivity analysis
Skin Infections	Proportion of patients developing skin infections requiring antibiotic treatment	Fisher's exact	ITT	Bari 4-mg or Bari 2-mg or Bari 1-mg vs PBO; Week 16	Secondary analysis

Abbreviations: ANCOVA = analysis of covariance; Bari = baricitinib; ITT = intent-to-treat; mLOCF = modified last observation carried forward; MMRM = mixed model repeated measures; NRI = nonresponder imputation; PBO = placebo; pMI=placebo multiple imputation; PPS = per protocol set..

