6.14.5.6. Infections

Infections will be defined using all the PTs from the Infections and Infestations SOC as defined in MedDRA. Serious infection will be defined as all the infections that meet the SAE criteria.

The number and percentage of patients with TEAEs of infections, serious infections, and infections resulting in permanent study drug discontinuation will be summarized by treatment group using MedDRA PTs. The proportion of patients developing skin infections requiring antibiotic treatment by Week 16 will also be summarized on the overview of infections table.

The number and percentage of patients with TEAEs of infections by maximum severity will be summarized by treatment group using MedDRA PTs.

Treatment-emergent infections will be reviewed in context of other clinical and laboratory parameters via a listing (details see Compound level safety standards).

The TEAE infections will be further analyzed in terms of potential opportunistic infection, herpes zoster and herpes simplex. Summary of HBV DNA monitoring results and association between infection and neutropenia/lymphopenia will also be provided in the context of infections.

Opportunistic infection

To identify potential opportunistic infections (POIs), the following approach will be used:

- identifying the POIs using a list of MedDRA PTs (refer to the compound level safety standards).

Potential opportunistic infections is identified through these search approaches and may be combined in one list for medical assessment and final classification of whether the case met the modified Winthrop definitions for OI.

A final listing for OIs will be provided for the CSR and to assist the composition of patient narratives.

Herpes zoster

Cases of herpes zoster will be further classified as follows:

- localized or non-multidermatomal-involvement of the primary and/or adjacent dermatomes only
 - complicated – documented ocular (cornea or deeper structure; for example, iritis, keratitis, retinitis, etc.) or motor nerve involvement (e.g., palsy; post herpetic neuralgia [PHN] does not meet criteria for motor nerve involvement).
 - uncomplicated-localized or non-multidermatomal cases that are not complicated
- multidermatomal-involvement beyond primary and adjacent dermatomes (that is, >3 contiguous dermatomes) or involvement of two or more non-contiguous dermatomes

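### Rescue censoring and nonresponder imputation reach the skin-infection endpoint, a harm for which the SAP never defines non-response

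*SAP*

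**What the plan says.** Section 4.2.2 lists "Proportion of patients developing skin infections requiring antibiotic treatment by Week 16" under an objective that compares the efficacy of each dose with placebo. Table JAHM.6.5 carries it as a secondary efficacy analysis in the ITT population, each dose against placebo at Week 16. The method column says Fisher's exact and nothing more.

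Three general rules apply to categorical efficacy endpoints:

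- **Censoring (Section 6.4).** The primary rule "will censor efficacy and health outcome data after permanent study drug discontinuation or after rescue therapy". On scope: "This censoring rule will be applied to all continuous and categorical efficacy and health outcome endpoints".
- **Imputation by table.** Table JAHM.6.1 assigns NRI under the primary censoring rule to "All remaining categorical measures". Section 6.11.2 sends secondary endpoints to that table.
- **Imputation by text (Section 6.4.1).** "All categorical endpoints will utilize the NRI method after applying the primary censoring rule". On meaning: "A NRI method imputes missing values as non-responses". Patients with no post-baseline observation are nonresponders at every visit.

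The same proportion appears again under safety in Section 6.14.5.6: "The proportion of patients developing skin infections requiring antibiotic treatment by Week 16 will also be summarized". Section 6.14 bases safety analyses on data before and after rescue by default, in the safety population.

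**The concern.** NRI is built for endpoints where success is the event, so the unfavourable value is obvious. Here the event is a harm. Setting a patient to non-response could mean infected (the unfavourable outcome) or not infected (the event did not occur). The SAP does not choose, so two programmers could follow it faithfully and produce opposite codings.

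The censoring rule raises a separate problem. Infections after rescue or permanent drug discontinuation are dropped, and Fisher's test on simple proportions ignores the shortened time at risk. If rescue is commoner in one arm, that arm loses more infections.

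At stake is one between-arm comparison of a clinically relevant harm, and the report could show two differently derived figures under one label.

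**Working it through.** **Plan's own figure.** The SAP gives no infection rate, rescue rate or power for this endpoint, so there is nothing to reproduce.

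**Inputs from the SAP.** 240 patients on placebo and 120 per baricitinib dose (Section 5.1); two-sided 0.05 (Section 6.2); Fisher's exact test (Table JAHM.6.5).

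**Assumptions.** True 16-week infection risk q = 5% in both arms (true ratio 1.0); constant infection hazard; a fraction r of each arm rescued, uniformly over the 16 weeks.

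**Step 1: infections seen before rescue.** With the 16 weeks as one unit of time, h = −ln(0.95) = 0.0513. The mean risk up to a uniform rescue time is m = 1 − (1 − e^(−h))/h = 1 − 0.05/0.0513 = 0.0252.

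**Step 2: censoring alone** (events after rescue dropped). Proportion = (1 − r)q + r·m.

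- Placebo, r = 0.50: 0.50 × 0.05 + 0.50 × 0.0252 = 3.8%
- Baricitinib, r = 0.30: 0.70 × 0.05 + 0.30 × 0.0252 = 4.3%
- Ratio about 1.13. In counts, about 9.0 of 12 expected placebo infections and 5.1 of 6 expected baricitinib infections are retained.

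**Step 3: worst case, rescued patients coded as infected.** Proportion = (1 − r)q + r.

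- Placebo: 0.50 × 0.05 + 0.50 = 52.5% (126/240)
- Baricitinib: 0.70 × 0.05 + 0.30 = 33.5% (40/120)
- Fisher p = 0.0007

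**Step 4: range over assumed rescue rates.**

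| Rescue, placebo vs baricitinib | Censoring alone, ratio | Rescued = infected, Fisher p |
|---|---|---|
| 50% vs 30% | 1.13 | 0.0007 |
| 40% vs 25% | 1.09 | 0.008 (34/120; 0.012 if 34.5 is rounded to 35) |
| 30% vs 20% | 1.06 | 0.09 |
| 50% vs 50% | 1.00 | no difference |

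**Step 5: false-rejection probability.** This is the exact Fisher rejection probability at 240 vs 120 with equal true infection risk. For these runs half of the rescued patients' infections are assumed to precede rescue.

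| Infection risk; rescue | All data used | Post-rescue infections dropped | Rescued = infected |
|---|---|---|---|
| 5%; 60% vs 40% | 0.038 | 0.046 | 0.915 |
| 5%; 70% vs 40% | 0.038 | 0.056 | 0.999 |
| 10%; 70% vs 40% | 0.040 | 0.074 | 0.999 |
| 5%; 50% vs 50% | 0.038 | 0.036 | 0.044 |

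With all data used, the test stays within 0.05. Dropping post-rescue infections raises it slightly. Only the rescued-means-infected coding breaks it, and only when rescue differs between arms.

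**The case against.** The best defence is that the specific row governs. Section 6.11 says Table JAHM.6.5 carries the method and imputation. Its responder rows name NRI, and the row for "Proportion of patients developing skin infections requiring antibiotic treatment" does not. Nor is every categorical measure imputed: in Table JAHM.6.7, WPAI employment status is summarised as observed. On that view no one intends to impute infections. Coding rescued patients as infected is the least natural reading, and a result above 50% would look absurd beside the infections overview.

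Much of this stands. It makes NRI doubtful for this endpoint and the worst case unlikely. It does not settle the matter. The employment row says observed and the infection row does not. The table is also not a dependable record of exceptions, since it gives SCORAD90 placebo multiple imputation and a tipping point while Table JAHM.6.1 gives it NRI only. Even if silence switches off imputation, the Section 6.4 censoring rule remains.

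A second defence is that counting only infections before rescue is a legitimate while-on-assigned-treatment estimand. It could be, but the SAP does not state it for this endpoint. Section 6.11.2 gives a different rationale, that response disappears after rescue, and a simple proportion labelled by Week 16 does not describe such an estimand.

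It is also true that the endpoint is outside the multiplicity procedure, and that an uncensored display of the same proportion is already planned under safety.

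**Conclusion.** The concern holds as a defect of specification with a modest expected bias. As written, the rules censor this harm endpoint at rescue or drug discontinuation and may impute a value that the SAP does not define. Under the assumed 5% risk and 50% against 30% rescue, censoring alone moves a true ratio of 1.0 to about 1.13. Milder rescue differences give 1.09 and 1.06, and equal rescue gives none.

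A reader might infer that the dose comparison would reflect rescue instead of infection. The SAP does not support that. It requires rescued patients to be coded as infected, which the SAP nowhere says, together with unequal rescue rates, which it does not give. The 52.5% against 33.5% result is a worst case conditional on both.

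The two displays of this proportion would still differ in derivation, with nothing to say which is definitive. The endpoint belongs to the other secondary objectives, so no primary or key secondary conclusion changes.

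**What to change.** In Sections 6.4 and 6.4.1, Table JAHM.6.1 and the skin-infection row of Table JAHM.6.5, state that this endpoint is exempt from the primary censoring rule and from NRI. Count every qualifying infection observed from first dose through Week 16, regardless of rescue or study drug discontinuation.

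State how patients not followed to Week 16 are handled. One option is observed events over the ITT denominator, supplemented by the incidence rate per patient-years of observation already defined in Section 6.14.2. This needs saying because post-treatment follow-up runs only to about 28 days after the last dose (Section 5.1), so ascertainment to Week 16 is not assured for early leavers.

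Use the same event derivation in Section 6.14.5.6, and note that the remaining difference between the two displays is the ITT against the safety population.

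The cost is a few sentences and one table row. The planned safety summary already uses post-rescue data, so the rescue part of the change needs no new data collection.

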6.4.2. Mixed Model for Repeated Measures

Mixed Model for Repeated Measures analyses will be performed on continuous endpoints to mitigate the impact of missing data. This approach assumes missing observations are missing-at-random (missingness is related to observed data) and borrows information from patients in the same treatment arm taking into account both the missingness of data through the correlation of the repeated measurements.

Essentially MMRM estimates the treatment effects had all patients remained on their initial treatment throughout the study. For this reason, the MMRM imputation implies a different estimand (hypothetical strategy [ICH E9 R1]) than the one used for NRI on categorical outcomes.

All continuous endpoints will utilize MMRM after applying the primary censoring rule. As sensitivity analyses, all secondary continuous endpoints will also utilize MMRM after applying the secondary censoring rule (Table JAHM.6.1).

6.4.3. Modified Last Observation Carried Forward

For continuous measure, a modified last observation carried forward (mLOCF) imputation technique replaces missing data with the most recent non-missing post-baseline assessment. The specific modification to the LOCF is data after an intercurrent event will not be carried forward thus the mLOCF is applied after the specified censoring rule is implemented. The mLOCF assumes the effect of treatment remain the same after the event that caused missing data as it was just prior to the missing data event. Analyses using mLOCF require a nonmissing baseline and at least 1 postbaseline measure otherwise the data is missing for analyses purposes. Analyses using mLOCF help ensure the number of randomized patients who were assessed post-baseline

is maximized and is reasonable for this data as data directly prior to an intercurrent event (such as initiation of rescue therapy or drop out) is likely a non-efficacious response.

All continuous efficacy and health outcomes endpoints will use with mLOCF imputation methodology with an ANCOVA as sensitivity analyses to the MMRM analyses.

